After determination of eligibility, participants will have a one-day CTRC admission for baseline laboratory studies, IVGTT, and body composition assessment (Study Visit 1) following an overnight fast. Upon arrival they will have an IV placed for blood draws and injections. Fasting blood glucose and insulin will be drawn at this time. Sex steroids and inflammatory markers will also be drawn at this time. (After the blood draw, they will undergo a frequently sampled IVGTT (specific methods for above described after Specific Aim 2). Up to 10 obese subjects will participate in the arm, as pilot subjects, who **are not** part of the treatment arm (i.e. they will not be taking a placebo).

In the afternoon of the Study Visit 1, a dual-energy x-ray absorptiometry (DEXA) scan will be performed to determine body composition. In a subset of participants (13 per group), soleus muscle nuclear magnetic resonance (NMR) and abdominal fast magnetic resonance imaging (MRI) sequence will also be performed to measure body fat distribution in terms of IMCL, liver fat content and visceral adipose content.

The next study visit (Study Visit 2) will occur when the participant has reached Tanner stage IV, approximately one year after the baseline visit. At this time the baseline laboratory draw, imaging studies and IVGTT will be repeated. For those subjects randomized to the MRI, it will not be repeated at this visit.

The next study visit (Study Visit 3) will occur when the participant has reached Tanner stage V, approximately one year after Study Visit 2. At this time the baseline laboratory draw, imaging studies and IVGTT will be repeated. This is the last long visit for the lean subjects. The obese subjects will stop taking the study medication at this time point.

The next study visit (Study Visit 4) will occur 6 months after the obese participants have reached Tanner stage V. At this time the baseline laboratory draw, imaging studies and IVGTT will be repeated. This is the last long visit for the obese subjects. For those subjects randomized to the MRI, it will not be repeated at this visit.

Between the visits, participants will be asked to come in every 6 months for anthropometric measurements and Tanner staging. Obese participants in the treatment arm (randomized to either Metformin or placebo) will also be asked to come in quarterly for pill counts to measure medication compliance and to receive a refill on their medication.

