Fast Magnetic Resonance Imaging (MRI) sequence: Rapid MRI will be used to assess hepatic fat fraction by the modified Dixon technique, previously described (56). In this technique, in- and out-of phase images of the liver will be obtained using a 1.5 Tesla magnet. The subject will be placed in a supine position on the body coil. The scan parameters include relaxation time = 9.3 ms (in-phase) and 7.3 ms (out-of-phase), echo time = 4.2 ms (in-phase) and 2.1 ms (out-of-phase), flip angle = 30 degrees, slice thickness = 10 mm, field of view = 32 x 16 cm, matrix size = 256 x 128, and number of excitations = 8. Four image slice pairs (in- and out-of-phase) will be obtained through the liver. Fat fraction will be calculated from the mean pixel signal intensity (SI) using the formula: Fat fraction = $(SI_{inphase} - SI_{outofphase}) / (SI_{inphase} + SI_{outofphase})$. A single slice at the level of the umbilicus will be used for determination of abdominal adipose distribution. Fast spin coil with a flip angle of 70 degrees, repetition time = 120 ms, echo time = 1.6 ms, field of view = 36 x 27 cm, slice thickness = 5.0 mm, matrix = 256 x 128, and number of excitations = 1.

Nuclear Magnetic Resonance Imaging (NMR): [name], of UCHSC radiology, will perform soleus NMR on a 3.0 T whole-body MRI scanner (GE Medical Systems, Waukesha, WI). The subject is positioned in the MR magnet feet first, prone, with the soleus muscle centered in the extremity coil. Scout images (usually T1-weighted) position the volume-of interest (usually 2cm x 2cm x 2cm), to avoid regions of gross adipose and vascular structures. Spectroscopy acquisition is performed using the PRESS pulse sequence without water suppression (TR/TE = 2000/24 ms, 64 averages, total acquisition time 2 minutes), and analyzed by SAGE spectroscopy analysis (GE). The water peak is fit as a Lorentzian line using Marquardt routine, and subtracted from the spectrum. The remaining peaks (creatinine and choline) are then fit using the Marquardt routine. IMC and EMC triglyceride peaks (1.3 and 1.5 ppm, respectively) are obtained from the fit results, corrected for T1 and T2 relaxation, and expressed as a percentage of the water content (96). Subjects need to hold reasonably still during the scan and cannot weigh >300 lbs.

All of the preceding imaging studies avoid radiation exposure and are regularly available at our institution.

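### The liver fat fraction formula in the MRI methods returns the fat-to-water ratio, which overstates the two-image fat fraction increasingly as liver fat rises; a small fix to a subset measure

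*Combined protocol and SAP*

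**What the plan says.** All references are to the combined protocol and SAP, Section D.

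- **What is measured.** The paragraph on the fast MRI sequence (Specific Methods) states: "Rapid MRI will be used to assess hepatic fat fraction by the modified Dixon technique, previously described (56". In-phase and out-of-phase images are taken at four slice positions.
- **How it is calculated.** "Fat fraction will be calculated from the mean pixel signal intensity (SI) using the formula" introduces the formula "Fat fraction = $(SI_{inphase} - SI_{outofphase}) / (SI_{inphase} + SI_{outofphase". The denominator is the sum of the two signals. No later conversion or other definition of liver fat appears.
- **Acquisition.** "echo time = 4.2 ms (in-phase) and 2.1 ms (out-of-phase". No relaxation correction is stated for the liver.
- **Contrast with muscle.** The next paragraph, on soleus spectroscopy, corrects the lipid peaks for relaxation and has them "expressed as a percentage of the water content (96". Where the plan intends a ratio to water, it says so.
- **Who and why.** Under the Specific Aim 1 Approach: "In a subset of participants (13 per group), soleus muscle nuclear magnetic resonance (NMR) and abdominal fast magnetic resonance imaging (MRI) sequence" are done "to measure body fat distribution in terms of IMCL, liver fat content and visceral adipose content".
- **When.** The same Approach says of both Study Visit 2 and Study Visit 4: "For those subjects randomized to the MRI, it will not be repeated at this visit". That leaves Study Visits 1 and 3, as in the visit tables. The Specific Aim 2 Approach numbers the visits differently and calls the end-of-treatment visit Study Visit 2.

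**The concern.** The quantity named and the quantity calculated are not the same. A fraction has all the signal, water plus fat, in its denominator. The stated denominator reduces to twice the water.

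The formula shows this at its limit. If water and fat contribute equally, the out-of-phase signal is zero and the formula gives 100%, although only half of the signal is fat.

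The discrepancy grows with the amount of fat, so it does not cancel between obese and normal-weight groups or between visits. Liver fat serves Aims 1b and 2b, which compare changes in fat distribution between groups. The background section gives fatty liver as a reason to look, and the preliminary data report a better ultrasound liver score on metformin. A reader would take a published value as a fraction and compare it with other fractions.

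**Working it through.** The plan gives no liver-fat value, so there is no figure of its own to reproduce. The check is algebra on the stated formula.

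**Inputs.** The formula and echo times come from the fast MRI paragraph. The signal model is an assumption, since the cited technique paper was not consulted: with water W and fat F, IP = W + F and OP = W − F, for F < W.

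**Step 1. What the formula returns.**
- IP − OP = 2F and IP + OP = 2W
- Stated formula: r = 2F/2W = F/W
- Fat fraction: f = F/(W + F) = (IP − OP)/(2 × IP)
- With W + F = 1: r = f/(1 − f), too high by a factor 1/(1 − f), or by f²/(1 − f) in absolute terms

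**Step 2. Size in the ideal case.**

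| Fat fraction f | Stated formula f/(1 − f) | Excess (points) |
|---|---|---|
| 5% | 0.05/0.95 = 5.3% | 0.3 |
| 10% | 0.10/0.90 = 11.1% | 1.1 |
| 20% | 0.20/0.80 = 25.0% | 5.0 |
| 30% | 0.30/0.70 = 42.9% | 12.9 |
| 40% | 0.40/0.60 = 66.7% | 26.7 |

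These liver-fat levels are illustrative; the documents give none.

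**Step 3. Differences and changes.**
- Groups at 20% and 5%, a gap of 15 points: 25.0 − 5.3 = 19.7 points
- Fall from 20% to 10%, 10 points: 25.0 − 11.1 = 13.9 points
- Fall from 30% to 20%, 10 points: 42.9 − 25.0 = 17.9 points

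For F < W the stated value rises steadily with f, so ranks at a single visit are unchanged. Means, changes and linear correlations are not preserved.

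**Step 4. Does the reading exceed the true value?** Not necessarily. The in-phase echo (4.2 ms) is later than the out-of-phase echo (2.1 ms), so T2* decay lowers IP more. With IP multiplied by exp(−4.2/T2*) and OP by exp(−2.1/T2*), an assumed liver T2* of 15 to 40 ms and no T1 effect:

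| True fraction | Stated formula | (IP − OP)/(2 × IP) |
|---|---|---|
| 10% | 4.2% to 8.5% | 4.0% to 7.8% |
| 20% | 18.3% to 22.5% | 15.5% to 18.4% |
| 30% | 37.0% to 40.7% | 27.0% to 28.9% |

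Both formulas are pulled down. On the same images their ratio is 2 × IP/(IP + OP), which is above 1 whenever IP > OP.

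**Step 5. Is the conversion exact?** From r = (IP − OP)/(IP + OP), 1 + r = 2 × IP/(IP + OP), so r/(1 + r) = (IP − OP)/(2 × IP). This is an identity for any pair of intensities. It equals f only under the signal model with F < W.

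**The case against.** The algebra is hard to dispute. The case on the other side concerns reach and consequence, and most of it stands.

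- **Liver fat is peripheral to the main analysis.** It is one of three MRI/NMR measures beside intramyocellular lipid and visceral fat, neither of which uses this formula. It is taken in 13 per group. The sample size rests on insulin sensitivity alone. The regression outcomes are insulin sensitivity, secretion and disposition index, and the named covariates are sex and changes in percent body fat and BMI. A reader might infer that the trial's main conclusions are at risk; the documents do not support that.
- **Overstatement is relative.** A reader might infer that every reported value will exceed true liver fat. Step 4 shows otherwise at low fat. The two images also carry different times of 9.3 and 7.3 ms; if these are repetition times, T1 weighting could push readings the other way. What stands is the excess over the two-image fat fraction from the same scans.
- **No cut-off is at stake.** A reader might expect misclassified fatty liver, but no planned analysis or eligibility rule uses a liver-fat threshold.
- **The source is cited.** The formula may be a transcription slip or the cited method's own index, and the documents do not show which formula was used on the data. The mismatch between label and calculation remains either way.

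**Conclusion.** The point holds as a labelling and scaling error. Followed as written, the plan reports a fat-to-water ratio under the name fat fraction. The excess is negligible at 5% (0.3 points), is 5.0 points at 20% and 12.9 points at 30%.

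The result rests on the basic in-phase/out-of-phase model with fat below half the signal. Above that, magnitude images make the stated formula return W/F, and neither formula recovers the fraction.

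The consequence is that differences and changes in points are enlarged where livers are fatty. The spread is enlarged too, so the effect on a test statistic could go either way. In the randomized comparison both arms pass through the same formula, so it rescales an effect rather than creating one where the arms do not differ. The grade is moderate to minor: a real correction to one subset measure of Aims 1b and 2b.

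**What to change.** 1. Replace the formula with (SI in-phase − SI out-of-phase)/(2 × SI in-phase). Equivalently, keep the stated ratio r, call it a fat-to-water ratio, and report r/(1 + r) as the fraction.
2. Before any liver-fat analysis, recompute values already derived for the baseline and the end-of-treatment (Tanner V) scans from the stored intensities. If only ratios were kept, convert each one before averaging over slices or participants; converting a mean is not equivalent, because the relation is not linear.
3. Reconcile the visit numbering of the MRI between the Specific Aim 1 and Specific Aim 2 Approach texts, so that it is clear which scans are meant.
4. State that the liver signals are not corrected for relaxation, or describe the correction. The new formula does not remove that bias.

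The cost is one line of formula, a sentence or two of text and a recalculation. No new scans are needed, and the sample size and the insulin analyses do not change.

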The proportion of adolescents who are obese has been increasing markedly in developed countries in the past 20 years (1), with a parallel increase in the incidence of type 2 diabetes mellitus (T2DM), so much so that it has been dubbed an “epidemic” by the American Diabetes Association (ADA)(2). Obesity is thought to promote the development of T2DM and related disorders at least partly through the development of decreased insulin sensitivity, a condition in which maintenance of normal blood glucose requires higher than normal insulin concentrations (3;4). This results in hyperinsulinemia as the pancreas compensates by increasing insulin production. Overt T2DM develops when the pancreas is unable to compensate for IR by increasing insulin production to the levels necessary to maintain normal carbohydrate metabolism. This results in relative insulin deficiency, while circulating insulin levels may still be normal or elevated. Thus, progressive β -cell failure in insulin-resistant, primarily obese youth is proposed to be a critical factor in the pathophysiology of childhood T2DM. IR correlates with increasing body weight and decreasing physical activity, as well as increased deposition of fat in the visceral cavity and skeletal muscle (5;6).

Insulin Resistance in puberty

The vast majority of youth who develop T2DM are in mid-puberty at the time of clinical presentation (7;8). Puberty, similarly to pregnancy, is known to be a period of physiologic decrease in insulin sensitivity (9). Amiel et al (9), reported a 36% reduction in insulin sensitivity in pubertal non-diabetics when compared with pre-pubertal non-diabetics, using the hyperinsulinemic euglycemic clamp technique. Interestingly, insulin sensitivity of adult subjects does not differ from pre-pubertal children, suggesting that insulin sensitivity improves again after puberty. Multiple cross-sectional and limited longitudinal studies have verified this phenomenon (10-17). The largest study involved 357 hyperinsulinemic-euglycemic clamps performed on children in Tanner stages I (pre-pubertal) through V (fully pubertal) and was cross-sectional in nature (16).

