Lean subjects will be asked to undergo a total of 3 DEXA scans throughout the course of the study, and for those randomized to the MRI, they will be asked to undergo a total of 2 MRI's. Obese subjects will be asked to undergo a total of 4 DEXA scans through the study, and for those randomized to the MRI, they will

Visit Number	Puberty Exam	Height & Weight	Pill Count	OGTT	IVGTT	DEXA	MRI*	Total Time
Screening Visit	x	x		x				4 hr
Study Visit 1		x			x	x	x	5-8 hr
Short Visits (Every 3 months)	x	x	x					1 hr
Study Visit 2	x	x			x	x		5-8 hr
Study Visit 3		x			x	x	x	5-8 hr
Study Visit 4		x			x	x		5-8 hr

be asked to undergo a total of 2 MRI's.

Please see the tables below for a more detailed explanation of the study procedures.

Specific methodology that will be used in this study is described after Specific Aim 2

Treatment table for obese subjects:

*Only those in the group who are asked to have an MRI/MRS

[figure not shown]
No Treatment table for lean subjects/obese pilot no treatment subjects:

Visit Number	Puberty Exam	Height & Weight	OGTT*	IVGTT	DEXA	MRI/ MRS**	Total Time
Screening Visit	x	x	x				2-4 hr
Study Visit 1		x		x	x	x**	5-8 hr
Short Visits	x	x					1 hr
Study Visit 2	x	x		x	x		5-8 hr
Study Visit 3	x	x		x	x	x**	5-8 hr

*Only participants who are overweight

**Only those in the group who are asked to have an MRI/MRS

Fig. 2 Timeline of Study Participation

metformin during puberty will help these individuals recover insulin sensitivity at the end of puberty, decrease compensatory hyperinsulinemia, and preserve insulin secretion, thereby improving their disposition index (DI).

SPECIFIC AIM 2:

2. To compare changes in insulin sensitivity and secretion and their correlates in obese adolescents treated with metformin or placebo during puberty.
 - a. To compare changes in insulin sensitivity, secretion and DI from early puberty to puberty completion between obese controls and obese adolescents treated with metformin.
 - b. To compare changes in body composition, fat distribution, and inflammatory markers over time between these groups.

RATIONALE:

The goal of this aim is to see whether treatment with metformin can improve insulin sensitivity and reduce compensatory insulin secretion during puberty. The thought is that, by improving insulin sensitivity and decreasing insulin secretion requirements during this temporary critical period of reduced insulin sensitivity,

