The CTRC study visit described previously for Study Visit 1 will be repeated twice more: at the end of this treatment period (Study Visit 2) and six months after the treatment is stopped (Study Visit 3). IVGTT, DEXA, abdominal fast MRI and soleus muscle NMR will also be repeated. We anticipate that the majority of patients will be Tanner stage V (T5) at the end of the 2-year treatment period, as the average time from the onset of breast development until menarche is 2-3 years. If T5 has not been reached after two years, the treatment will continue until the individual is at T5. Follow-up visits for Tanner staging will occur quarterly.

The final visit (Study Visit 3) will be to determine whether insulin sensitizing treatment will result in persistent improvement in insulin sensitivity and insulin secretion, even after treatment is stopped. The subjects will again be given a 3-day standard macronutrient diet and will fast overnight prior to admission. Only the IVGTT and anthropometric measurements will be performed at this study visit.

Specific Methods:

Screening laboratory studies: ALT, AST, electrolytes, fasting lipids, CBC, BUN and urinalysis.

Laboratory studies drawn at Visits 1, 2 and (for obese subjects only) 3: sex steroids, c-reactive protein (CRP), interleukin-6 (IL-6), adiponectin and fasting lipids. Sex steroids (free testosterone, estradiol,

androstenedione and DHEAS) will be drawn in order to confirm or refute previously found associations between sex steroids and IR. Inflammatory markers and other factors that have been associated with IR will also be drawn at this visit, including c-reactive protein, interleukin-6, adiponectin and fasting lipids (LDL, HDL and triglycerides).

Anthropometric measurements: Height, weight, waist-to-hip ratio, and supine abdominal height are measured by standard techniques.

Oral Glucose Tolerance Test: Glucose and insulin drawn at fasting (0), and at 30, 60, 120 and 180 minutes after ingestion of glucola (1.75g/kg, max 75g)

Dual-energy X-ray absorptiometry (DEXA Scan): Body composition will be measured supine using the DEXA technique on the pediatric CRC and will be used to derive fat-free mass (92). This technique relies on the absorption of dual electron wavelengths for the assessment of body fat, lean tissue, and bone mineral density.

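### The imaging methods call all listed studies radiation-free although DEXA is X-ray, the DEXA schedule contradicts itself, and pregnancy during follow-up is not addressed

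*Combined protocol and SAP*

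**What the plan says.** Section D, Specific Methods, describes three imaging methods in sequence: DEXA, fast MRI and soleus NMR. It then closes the list with "All of the preceding imaging studies avoid radiation exposure and are regularly available at our institution". The first entry reads "Dual-energy X-ray absorptiometry (DEXA Scan): Body composition will be measured supine using the DEXA technique", and its description continues: "This technique relies on the absorption of dual electron wavelengths for the assessment of body fat, lean tissue, and bone mineral density". The Specific Aim 1 Approach also names the method in full: at Study Visit 1, "a dual-energy x-ray absorptiometry (DEXA) scan will be performed to determine body composition".

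On frequency, the Specific Aim 1 Approach says "Lean subjects will be asked to undergo a total of 3 DEXA scans throughout the course of the study" and "Obese subjects will be asked to undergo a total of 4 DEXA scans through the study". Only MRI and NMR are confined there to a subset of 13 per group. The Specific Aim 2 Approach says of the post-treatment visit: "Only the IVGTT and anthropometric measurements will be performed at this study visit". Section A, under both aims, says body composition is examined in a subset of participants.

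On pregnancy, section B (Insulin Resistance in puberty) says "Puberty, similarly to pregnancy, is known to be a period of physiologic decrease in insulin sensitivity", and repeats the idea later in the same subsection when it explains compensatory insulin secretion. Exclusions a to l under Specific Aim 1 do not name pregnancy, and Specific Aim 2 adopts that list by reference. No pregnancy test appears in the screening or visit laboratory lists, the visit tables, the imaging methods or the IVGTT preparation. The Statistical analysis section has no rule for an IVGTT taken during pregnancy.

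**The concern.** Two things follow from the text. First, a methods section assigns a safety property to a procedure that does not have it, in a study that enrols children from age 9, and nothing elsewhere in the supplied text corrects it. A reader relying on that sentence would not look for the precautions that go with repeated X-ray scans.

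Second, once DEXA is acknowledged as X-ray, the eligibility and visit procedures need to be read against it and against section B. Girls are followed to Tanner V, and obese girls for six months beyond. The Specific Aim 2 Approach puts menarche on average 2–3 years after the onset of breast development, and treatment lasts two years or until Tanner V if later, so follow-up past menarche is to be expected. The plan as written would allow a DEXA scan and an endpoint IVGTT during an undetected pregnancy. Such an IVGTT would show reduced insulin sensitivity for a reason other than obesity or treatment, in the same direction as the failure to recover that Hypothesis 1 predicts.

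**Working it through.** **1. Radiation statement against the list it closes.** The studies preceding the sentence are DEXA, MRI and NMR. DEXA is named as X-ray absorptiometry in the Specific Aim 1 Approach and in Specific Methods. The statement can hold for MRI and NMR but not for DEXA. The DEXA entry is also at odds with itself: its title says X-ray, while its description speaks of electron wavelengths.

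**2. The plan's own scan count.** The visit table for treated obese participants marks DEXA at Study Visits 1, 2, 3 and 4, which is 4 scans. The table for lean and untreated obese pilot participants marks Study Visits 1, 2 and 3, which is 3 scans. Both match the stated 3 and 4. With 52 normal-weight and 104 obese participants:

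- As stated: 52 × 3 + 104 × 4 = 156 + 416 = 572 scans.
- If the up to 10 untreated obese pilots lie within the 104 and have 3 each: 52 × 3 + 94 × 4 + 10 × 3 = 156 + 376 + 30 = 562.

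**3. The same count under the conflicting text.**

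- Four obese visits, but no DEXA at the last: 52 × 3 + 104 × 3 = 468.
- The Specific Aim 2 schedule taken alone (baseline, end of treatment, six months after; no DEXA at the last): 2 scans per obese participant, so 52 × 3 + 104 × 2 = 364.
- Body composition in a subset only, as in section A: not countable, because no subset size is given for DEXA.

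All of these are before dropout, which the Sample size calculation puts at 30%. Every version keeps DEXA in the study, so the error in step 1 does not depend on which count is right.

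**4. Where pregnancy could be caught.** Exclusion l lets the investigator exclude for another significant illness or condition. It does not name pregnancy, no test supports it, and it operates at entry. Entry requires Tanner II–III, when pregnancy would be rare. The later stages, where it is less unlikely, have no corresponding provision.

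**5. Possible size of the endpoint effect.** The documents give no pregnancy rate and no size for the fall in insulin sensitivity. The following range is an assumption: a proportion q of 1–5% of a group affected, each with a fall d of 1–2 units (min⁻¹ per µU/ml × 10⁻⁴).

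- Shift in that group's mean change = q × d, from 0.01 × 1 = 0.01 to 0.05 × 2 = 0.10. The planned metformin versus obese-control difference is 1.16 − (−0.17) = 1.33.
- Power as planned: means 1.16, −0.17 and 1.6, SD 1.85, 30 per group, one-way ANOVA at 0.05. The grand mean is 0.863 and the sum of squared deviations is 1.70, so the noncentrality is 30 × 1.70 / 1.85² ≈ 14.9 on 2 and 87 degrees of freedom. Power is 93.5%, which reproduces the stated 93%.
- Power with the added variance alone: SD = √(1.85² + q(1 − q)d²). For q = 0.01 and d = 1 this is 1.853, with power 93.4%. For q = 0.05 and d = 2 it is √(3.4225 + 0.19) = 1.901, with power 92.1%.

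**The case against.** The strongest reply is that this is loose drafting. The sentence sits directly after the MRI and NMR paragraphs, the X-ray nature of DEXA is in its name, and a one-line edit settles it. It stands that nothing was concealed and that the edit is small. It does not stand that the sentence can be read as excluding DEXA: it says all, and DEXA heads the list.

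It is also fair to say that the wrong sentence and the missing pregnancy provision are separate matters. A reader might infer that pregnancy was left out because the imaging was believed to be radiation-free. No text says so, and that link should not be drawn. The connection is only that correcting the first makes the second need attention.

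Three other strong readings go too far:

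- That all 156 participants certainly have 3 or 4 scans: this rests on the Specific Aim 1 Approach and tables, and other text contradicts it.
- That a pregnant girl would meet every criterion: exclusion l gives the investigator some discretion at entry.
- That participants were not told of radiation or pregnancy procedures: the consent pages are not in the file, so this cannot be judged.

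The objection that the effect on the endpoint is small is correct. It limits the point, but leaves the incorrect safety statement and the follow-up gap in place.

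**Conclusion.** The radiation statement is wrong on the protocol's own text, whichever scan schedule applies. The schedule is internally inconsistent: up to 572 planned scans before dropout on the fullest reading, 562 if the untreated pilots lie within the 104, and fewer on the Specific Aim 2 or subset wording. The supplied text names no pregnancy exclusion or test, and the gap that matters is pregnancy arising during follow-up rather than at entry.

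A reader might go on to conclude that the insulin-sensitivity results are materially at risk. The documents do not support that. On the assumed range the shift in a group mean is 0.01–0.10 units, and power stays at about 92–93%. The shift affects a comparison only to the extent that pregnancies are unequal between groups. The weight of the point lies in the safety wording and the missing safeguard. It concerns the protocol and analysis text only, and the radiation dose cannot be sized because no DEXA dose is given.

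**What to change.** - **Imaging text.** Limit the no-radiation sentence to MRI and NMR, and correct the DEXA description so that it agrees with the method's name.
- **Schedule.** Reconcile the Specific Aim 1 Approach and visit tables, the Specific Aim 2 text on the last obese visit, and the subset wording in section A. State one DEXA schedule per group, with consistent visit numbers. Which schedule is right is for the sponsor to say.
- **Pregnancy.** Reconcile eligibility and visit procedures with the use of X-ray and with section B. A urine pregnancy check for girls past menarche at the existing DEXA/IVGTT visits would close the follow-up gap. The rules for eligibility, scans and study medication in pregnancy are for the sponsor to define.
- **Analysis.** State in advance that an IVGTT taken during pregnancy is not used as an end-of-puberty or post-treatment value, and add a sensitivity analysis that includes it. The second part matters because pregnancy is a post-randomisation event in the metformin comparison, and the analysis section names no method for missing values.

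The cost is protocol wording, a small additional urine collection (urinalysis is listed only at screening), a procedure for confidential handling of results in minors, and probably very few missing endpoint values.
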